8.0 REFERENCES	

Affected Section(s)	Summary of Revisions Made	Rationale
3.2; 3.3; 3.4; 3.5; 4.0; 5.3	Study inclusion and exclusion criteria were further specified (3.2 and 3.3). Study recruitment process and strategies were further explained and described (3.5). One more study questionnaire was added (4.0). Variables to be collected were described in details (5.3).	Changes were made internally to provide more details about the study particularly about the recruitment process.
3.3; 3.5	Two study exclusion criteria omitted (3.2 and 3.3). New recruitment method added (3.5).	Changes were made internally to include a larger potential cohort and make patient identification easier for study staff and referring providers.

SUMMARY OF CHANGES FROM PREVIOUS VERSION:

PROTOCOL SUMMARY

Purpose

- Examine the feasibility of using Virtual Reality (VR) software VR Solace as a method for treating any-cause chronic pain in hospitalized patients

- Compare physiological changes during use of VR Solace to patient reported outcomes (PROs).

✤ Aims

1) To assess the effects of VR Solace on pain and anxiety as reported by the Numeric Pain Rating Scale (NPRS) and the State-Trait Anxiety Inventory 6 (STAI-6), respectively

- Measure the subsequent therapeutic response using validated survey data

- Analysis of demographic characteristics and survey data will be conducted to identify factors associated with greater therapeutic responses to VR Solace in patients with pain

Evaluate associations between medical history/lab values to patient PROs
2) To investigate any correlations between physiological changes during VR Solace use (heart rate, heart rate variability, and pupil diameter) and patient-reported outcomes.

- Demonstrate presence of physiological effects with VR Solace use
- Evaluate which physiological effects are associated with greater therapeutic response
- Research Procedures
 - Validated survey to assess pain and anxiety pre-VR
 - Administer VR Solace to patients
 - Collect real-time biodata during VR Solace session of 15 minutes
 - Repeat surveys post-VR
 - Data analysis
- Subject Population
 - Patients currently admitted at Cedars-Sinai Medical Center with chronic pain, independent of admitting diagnosis
- Duration
 - 1 visit per subject
 - Total study period of 3 months

GENERAL INFORMATION

- CSMC Co-Investigators
 - All listed on cover page
 - Any other residents to be involved
- Sponsor/Funder
 - This study is not funded
- Collaborating Institutions Involved in the Research
 - Not applicable

1.0 BACKGROUND, RATIONALE

Chronic pain is commonly reported in clinical settings, affecting over 20% of the global population.¹ Several studies previously estimated the prevalence of chronic pain to range from 11% to 40% of adults in the United States.² Despite significant improvements in medications, procedural interventions, and noninvasive therapies, persistent pain is detrimental to the functional status and psychological well-being of individuals in the community. Furthermore, pain and anxiety have been shown to co-occur in many individuals, and nearly 50% of patients with chronic pain suffer from one or more anxiety disorders.³ This association is seen across multiple clinical settings and major life domains,⁴ and healthcare for its surveillance and treatment is costly and resource-intensive.⁵

Virtual Reality (VR) was first effectively used to treat pain in 1998,⁶ and since has become an emerging treatment modality for numerous indications. Its efficacy in treating pain and anxiety

has been demonstrated in acute, surgical or procedural settings,^{7, 8} as well as in chronic conditions including cancer.⁹ Success of improving mood, stress levels, and pain relief with VR has been repeatedly achieved, and implementation of VR is steadily growing in the field. Despite the increasing use of VR as non-invasive, additive therapy, there are limited studies of VR efficacy exploiting validated survey data from patients in the inpatient setting.¹⁰ Along with patient-reported outcomes, real-time physiological changes have been observed to measure responses to VR use. The physiological changes include gaze tracking, heart rate, skin temperature, respiration rate, blood pressure, and among others.¹¹ In current literature, very few studies have examined the correlation between real-time physiological changes and patient-reported survey data. In detail, the studies were conducted in limited context such as acute ICU care or use of simple biodata such as oxygen saturation.^{12, 13}

Therefore, the purpose of this prospective, observational study is to assess the therapeutic response to VR Solace in patients with chronic pain and anxiety using real-time clinical and survey data. Secondly, with use of relatively more complex biodata, this study can establish a possible association between the patient-reported changes in pain or anxiety levels with several real-time physiological measurements during VR Solace use. This study hopes to pave way not only in developing a standard VR therapy regimen for chronic pain and anxiety, but also in formulating a prediction of an individual's therapeutic response to VR based on biodata and clinical factors.

2.0 STUDY OBJECTIVES

The purpose of this study is to assess the therapeutic response to VR Solace in patients with chronic pain and anxiety using real-time clinical and survey data. Regression analysis of demographic characteristics, lab and survey data will be conducted to better understand the efficacy of VR Solace in treating chronic pain and anxiety. We also aim to explore the possible association between the patient-reported changes in pain or anxiety levels with real-time physiological changes observed during VR Solace use.

3.0 STUDY POPULATION

3.1 SELECTION OF THE STUDY POPULATION

- Will be conducted at one site only, inpatient hospital setting at Cedars-Sinai Medical Center

- 3.2 INCLUSION CRITERIA
 - Age 18+
 - Patient-reported or physician-diagnosed (ICD-10 codes) chronic pain defined as: persistent or recurrent pain lasting *longer than 3 months*
 - Chronic pain can be classified in 7 subtypes: (1) chronic primary pain, (2) chronic cancer pain, (3) chronic posttraumatic and postsurgical pain, (4) chronic neuropathic

pain, (5) chronic headache and orofacial pain, (6) chronic visceral pain, and (7) chronic musculoskeletal pain.

1. Primary pain: Pain in 1 or more anatomic regions that persists or recurs and is associated with significant emotional distress or significant functional disability and that cannot be better explained by another chronic pain condition.

2. Cancer pain: Pain caused by cancer itself and/or pain from cancer treatment.

3. Posttraumatic and postsurgical pain: Pain after a tissue injury from trauma or surgical procedure

4. Neuropathic pain: Pain and sensory signs along neurodistribution that is anatomically plausible, with previous history of nerve injury at site of lesion

5. Headache and orofacial pain: Pain for at least 50% of the days in the 3-month period.

6. Visceral pain: Pain from the internal organs of head and neck region, and thoracic, abdominal, and pelvic cavities.

7. Musculoskeletal pain: Pain directly from bone, joint, muscle, or related soft tissue

- Endorsing acute pain during admission, within last 24 hours, a measurement of 3 or greater on 11-point scale on validated survey during hospital stay
- Chronic pain does not need to be primary diagnosis of admission

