3.4 SUBJECT SCREENING AND ENROLLMENT

- Data will be prospectively collected during the study period
- Gauge interest from Pain Service Team at Cedars-Sinai Medical Center in collaborating to identify prospective patients

- Primary investigators listed on the cover page will access the records needed for screening
- Medical records will be reviewed for purposes of screening: Age – 18+ Pain Score documented per nursing Medications/Treatments – Beta Blockers

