4.0 STUDY DESIGN AND METHODS

Collection of Survey Data

 \rightarrow *Primary outcomes*: Evaluate for treatment response in pain/anxiety levels after VR Solace session (1 time)

- Validated pain survey
 - Pain Numeric Rating Scale (pre & post-VR)
- Validated anxiety survey
 - Full or 6-question abridged version of State-Trait Anxiety Inventory (pre & post-VR)

→ Secondary outcome: Assess for physiological changes during VR Solace use (heart rate, heart rate variability, and pupil diameter)

- Compare the average physiologic measures (3 listed above) of the first minute with average of last minute of VR use (15 minutes total, not including pre- and post-VR survey time)
- Correlation of the changes in average and survey data/patient-reported outcomes
- \rightarrow *Covariates*: Consider using these survey variables as covariates in multivariable regression models
- System Usability Scale subjective assessments of device/system usability
- Simulator sickness questionnaire (SSQ) Assessing motion sickness + presence survey
- Immersive Tendencies Questionnaire

✤ Collection of Biodata

 \rightarrow Directly from VR Solace device

• Heart rate, heart rate variability, pupil diameter changes – calculation of averages

• Use as covariates in multivariable regression models

Data Analysis

- → Multivariable linear regression models
 - Change in pain/anxiety scores as outcomes continuous variable
 - Covariates of demographic factors, comorbidities, biodata, other survey data (System Usability Scale, Immersive Tendencies Questionnaire)

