7.0 STATISTICAL CONSIDERATIONS

7.1 STUDY OUTCOME MEASURES

Outcomes will be continuous—change in pain/anxiety levels in response to VR Solace treatment session. The levels will be measured by validated scales, and changes will be calculated based on pre-session and post-session survey responses. Secondary outcomes will also be continuous, as change in averages of first and last minute of the VR Solace session (not including pre- and post-VR survey time).

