7.2 SAMPLE SIZE CONSIDERATIONS

• A paired t-test was used to calculate power. The desired power is 80% and 0.05 was used as the significance level.

- To achieve a moderate to large effect of 0.5, we estimate to recruit a sample of 34 patients, and to achieve a larger effect of 0.8, we estimate to recruit a sample of 16 patients.
- No measures to decrease bias/precision such as blinding of staff will be performed, however study protocol will be followed strictly for all subjects in same hospital settings.

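### The entry pain score may be up to 24 hours old, so patients with little or no pain at the pre-VR survey can enter and show a small or zero pain change whatever the effect of VR

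*Combined protocol and SAP*

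**What the plan says.** Section 3.2 requires chronic pain, defined as "persistent or recurrent pain lasting *longer than 3 months", together with pain in the current stay: "within last 24 hours, a measurement of 3 or greater on 11-point scale on validated survey during hospital stay". Section 3.4 lists what is read from the medical record at screening, including "Pain Score documented per nursing".

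Section 4.0 makes the treatment response in pain and anxiety after a single session the primary outcome, with pain measured on the numeric scale before and after VR. Section 7.1 confirms that "changes will be calculated based on pre-session and post-session survey responses" and that the outcome is continuous. The Protocol Summary gives the session length as 15 minutes and one visit per subject.

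The regression models in section 4.0 take the change in pain or anxiety as outcome, with "Covariates of demographic factors, comorbidities, biodata, other survey data". The parenthesis that follows names the usability scale and the immersive tendencies questionnaire. The pre-VR pain score is not named.

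On sample size, section 7.2 states: "A paired t-test was used to calculate power". "The desired power is 80% and 0.05 was used as the significance level". It gives 34 patients for an effect of 0.5 and 16 for an effect of 0.8, with no mean change, SD or source behind either.

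**The concern.** A minimum pain score in a study of pain response serves to enrol people who have pain to treat. Here the minimum can be met by one reading at any time in the previous day, whereas the outcome depends on pain in the minutes around the session. Someone who scored 6 overnight and 0 or 1 at the pre-VR survey satisfies section 3.2. Recurrent pain counts as chronic pain, and section 5.3 collects opioid use, so pain that varies within a day is foreseeable.

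Two things are at stake. The first is the mean pain change, which such patients pull toward zero. The second is the search, under Aims 1 and 2, for characteristics and physiological signals associated with a greater response. The room to improve depends on the pre-VR score. If that score is left out of the model, anything that goes with low pain at session time, such as recent analgesia, can appear to predict a small change. This second consequence does not depend on the power calculation.

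**Working it through.** **1. The two measurements, side by side.**

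| | Qualifying score | Outcome baseline |
|---|---|---|
| Where | 3.2, 3.4 | 4.0, 7.1 |
| Source | Score in the record (nursing, per 3.4) | Study survey before VR |
| Timing | Any time in the last 24 hours | Just before the session |
| Minimum | 3 on an 11-point scale | None stated |

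No section requires a repeat check before the session or says how low pre-VR scores are handled. The largest possible fall equals the pre-VR score: 0 points from 0, 1 from 1, 2 from 2, 6 from 6. A patient at 0 can only stay level or worsen.

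**2. The plan's own figures.** For a paired t-test, power = P(|T| > t(0.975, n−1)), with T noncentral t, n−1 degrees of freedom and noncentrality d√n. Section 7.2 does not state sidedness. A two-sided test reproduces the plan; a one-sided test would give 27 and 12.

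- d = 0.5, n = 34: noncentrality 0.5 × √34 = 2.92, power 80.8%. The smallest n for 80% is 34.
- d = 0.8, n = 16: noncentrality 0.8 × 4 = 3.2, power 84.8%. The smallest n is 15 (82.1%).

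The stated 34 and 16 stand if every patient has pain at the session.

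**3. Dilution, extreme case.** Assume a share p has a change of exactly 0, and the rest have mean d and SD 1. The documents do not give p, so a range is shown.

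Mean = d(1−p). Variance = (1−p) + p(1−p)d². Effective effect = mean / √variance.

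Example, p = 0.2 and d = 0.5: mean 0.40; variance 0.80 + 0.16 × 0.25 = 0.84; effect 0.40/√0.84 = 0.436; power at n = 34 is 70%.

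**4. Dilution, milder case.** Assume instead that the low-pain share has half the mean change and half the SD.

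Mean = d(1−p/2). Variance = (1−p) + p/4 + p(1−p)d²/4.

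Same example: mean 0.45; variance 0.80 + 0.05 + 0.16 × 0.0625 = 0.86; effect 0.45/√0.86 = 0.485; power 78%.

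| p | Zero change, n=34, d=0.5: effect, power (n for 80%) | Zero change, n=16, d=0.8: effect, power (n for 80%) | Half change, n=34: power | Half change, n=16: power |
|---|---|---|---|---|
| 0 | 0.500, 81% (34) | 0.800, 85% (15) | 81% | 85% |
| 10% | 0.469, 76% (38) | 0.736, 79% (17) | 80% | 83% |
| 20% | 0.436, 70% (44) | 0.674, 71% (20) | 78% | 82% |
| 30% | 0.403, 63% (51) | 0.613, 63% (23) | 77% | 81% |

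These figures treat the mixture as normal. Simulation of the zero-change case gives power about 1 to 3 points higher.

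**5. Third case.** If the planned d describes the population admitted under section 3.2, low-pain patients included, the dilution is already inside d, and power stays at 81% and 85%.

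**The case against.** The strongest reply is that both the share of low-pain patients and the harm they do are unknown. The criterion permits them but does not show that they will be common, and p could be close to 0. The large power loss needs patients at exactly 0 with no change and a d that leaves them out. Smaller changes also carry a smaller variance, so under the milder model most of the loss disappears. All of this stands, and it limits the size of the point.

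Two stronger readings are tempting. A reader might infer that low-pain patients are counted as non-responders in Aims 1 and 2. The documents do not support this: sections 4.0 and 7.1 analyse change as a continuous variable, and there is no responder category. A reader might also infer that anyone with little pain cannot show a response. That is true only at a pre-VR score of 0; at 1 or 2 a fall is possible but capped.

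The source of the qualifying score is also less than certain. Section 3.2 speaks of a validated survey, while section 3.4 lists the nursing score for screening. That the nursing score alone satisfies 3.2 is the natural reading, but it is not stated. Neither section ties the score to the session.

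Finally, requiring a recent high score could time sessions to pain peaks, so that spontaneous decline enters the change in a study without a control group. This is a fair warning. It weighs most against using the pre-VR score itself for entry. In a simulation with assumed pain variability (the documents give none), selecting on a score 2 hours earlier produced a drift of about 0.01 to 0.03 points with no treatment effect, against 0.12 to 0.16 when selecting on the pre-VR score. It also cut the share with a pre-VR score of 0 or 1 from about 13-16% to 4-8%. These figures are illustrative only. A separate baseline limits regression to the mean but does not remove it.

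**Conclusion.** The gap is real. The entry threshold does not secure pain at the time the outcome is measured, and no section compensates in the analysis. The direction is clear: the mean pain change is pulled toward zero, and the regressions, without the pre-VR score, can attribute low baseline pain to whatever goes with it.

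The size is uncertain. With 10% to 30% of patients at 0 and no change among them, and a d that describes only the others, power falls to 76-63% at n=34 and 79-63% at n=16. With half the change and half the SD in those patients, it is 80-77% and 83-81%. If d already averages over them, nothing is lost. Section 7.2 gives no basis for choosing among these cases. The power loss is therefore a possibility to guard against, not a demonstrated shortfall. The confounding of the regressions is the firmer reason to act, since it needs only variation in pre-VR pain that is related to the factors studied.

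**What to change.** - In section 3.2, keep the existing threshold but apply it to the most recent nursing-documented score before the session. If that score is below the threshold, reschedule the session within the stay. Align the wording of 3.2 and 3.4 on which score qualifies.
- State that the pre-VR numeric rating is a separate baseline and is not used for entry.
- In section 4.0, name the pre-VR pain score as a covariate in the pain change models. Its own coefficient should not be read as a treatment effect, because it also carries regression to the mean.
- Report how many patients had pre-VR scores of 0, 1 or 2.

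The cost is one line in 3.2, a chart check on the day, one model term and one reported count. Some sessions would be moved and some otherwise eligible patients lost, including for the anxiety outcome, to which they would have contributed. If the entry change is judged too costly for recruitment, the covariate and the count can be adopted alone. They address the regressions and make the problem visible, but they do not restore the room to improve.

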3.3 EXCLUSION CRITERIA

- No active diagnosis of medical conditions that may cause physiological variations in vital signs (i.e. sepsis, cardiogenic shock/arrhythmia)
- No active diagnosis or undergoing treatment of primary GI cancer
- No active diagnosis of seizures, migraines, severe nausea, severe propensity for motion sickness, or facial/head deformities that would allow for comfortable placement of headset
- Exclusions of patient currently taken a beta blocker in the last 24 hours
- Unable to communicate/read English for survey items
- Unable to use VR independently patients will be expected to maneuver through questions/steps of the VR system during the session

3.4 SUBJECT SCREENING AND ENROLLMENT

- Data will be prospectively collected during the study period
- Gauge interest from Pain Service Team at Cedars-Sinai Medical Center in collaborating to identify prospective patients

- Primary investigators listed on the cover page will access the records needed for screening
- Medical records will be reviewed for purposes of screening: Age – 18+ Pain Score documented per nursing Medications/Treatments – Beta Blockers

3.5 SUBJECT RECRUITMENT

- Subjects will be from both investigators' patients and referrals from other care providers: General medicine wards team, Orthopedics, Gastroenterology inpatient, Pain Medicine team, Supportive Care team (SCM)
- Primary investigators listed on cover page along with other investigators of the project (currently recruiting other investigators) will approach subjects in person
- Patient referrals from other providers at Cedars-Sinai Medical Center
- No advertising will be used
- We will enlist Cedars-Sinai's Enterprise Information Services's (EIS) Honest Enterprise Research Brokers (HERB) Committee to identify inpatients that meet our inclusion criteria.

4.0 STUDY DESIGN AND METHODS

Collection of Survey Data

 \rightarrow *Primary outcomes*: Evaluate for treatment response in pain/anxiety levels after VR Solace session (1 time)

- Validated pain survey
 - Pain Numeric Rating Scale (pre & post-VR)
- Validated anxiety survey
 - Full or 6-question abridged version of State-Trait Anxiety Inventory (pre & post-VR)

→ Secondary outcome: Assess for physiological changes during VR Solace use (heart rate, heart rate variability, and pupil diameter)

- Compare the average physiologic measures (3 listed above) of the first minute with average of last minute of VR use (15 minutes total, not including pre- and post-VR survey time)
- Correlation of the changes in average and survey data/patient-reported outcomes
- \rightarrow *Covariates*: Consider using these survey variables as covariates in multivariable regression models
- System Usability Scale subjective assessments of device/system usability
- Simulator sickness questionnaire (SSQ) Assessing motion sickness + presence survey
- Immersive Tendencies Questionnaire

✤ Collection of Biodata

 \rightarrow Directly from VR Solace device

• Heart rate, heart rate variability, pupil diameter changes – calculation of averages

• Use as covariates in multivariable regression models

Data Analysis

- → Multivariable linear regression models
 - Change in pain/anxiety scores as outcomes continuous variable
 - Covariates of demographic factors, comorbidities, biodata, other survey data (System Usability Scale, Immersive Tendencies Questionnaire)

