5.0 DATA COLLECTION AND MANAGEMENT

5.1 DATA PROCUREMENT

- Biodata will be collected by the VR headset during the session.
- Patient-reported outcome data will be collected by surveys administered to the study participants.

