5.3 VARIABLES COLLECTED

The following data points/variables will be collected:

- Age
- Education
- Gender
- Employment
- Marital status
- Income
- Household size
- Primary admitting diagnosis
- Primary referral diagnosis (provider reported or ICD-10 coded)
- Race
- Ethnicity
- Surgical history (any pain related surgery)
- Social history drug/opiate use)
- Medications/treatments (opioids, MME, start date-end date for at least 3 months)
- Survey data (pre & post-VR session) described above
- Real-time biodata obtained through VR device heart rate, heart rate variability, pupil diameter changes

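### With no pre-VR reading of heart rate, heart rate variability or pupil diameter, the first-versus-last-minute contrast measures change during VR but cannot by itself show that physiological effects are present

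*Combined protocol and SAP*

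**What the plan says.** Section 4.0 defines the physiological outcome: "Compare the average physiologic measures (3 listed above) of the first minute with average of last minute of VR use". Section 7.1 repeats this as a change between the two one-minute averages and excludes survey time.

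The timing and source of the biodata are stated in several places. The research procedures in the Protocol Summary read "Collect real-time biodata during VR Solace session of 15 minutes". Section 5.1 reads "Biodata will be collected by the VR headset during the session". Section 5.3 lists "Real-time biodata obtained through VR device heart rate, heart rate variability, pupil diameter changes" and has no resting measurement of any of the three. The only pre-VR assessment in the procedures is by survey.

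The wording of the aim varies. The Aim 2 heading is "To investigate any correlations between physiological changes during VR Solace use" and patient-reported outcomes. Section 2.0 likewise speaks of an association "with real-time physiological changes observed during VR Solace use". The first sub-bullet under Aim 2 goes further: "Demonstrate presence of physiological effects with VR Solace use".

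**The concern.** Both windows of the contrast lie inside VR exposure. Pain and anxiety each have a value from before VR, but the physiological measures do not. To show that an effect is present, one needs a level to compare with, and the first minute of exposure is not an unexposed level.

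For the sub-bullet, a null first-to-last difference could mean that nothing happened, or that a response was fully present from the start and held. A non-zero difference shows that something changed, but not whether the patient moved away from rest or came back to it. Each patient has one visit, so a baseline that was not recorded cannot be obtained afterwards.

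**Working it through.** The plan gives no figure for this point. Section 7.2 names no physiological outcome for its effect sizes of 0.5 and 0.8 or its samples of 34 and 16. The check is therefore about what the contrast can identify.

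**Step 1: where the windows lie.** The session lasts 15 minutes (Protocol Summary; Section 4.0). The windows are minutes 0–1 and 14–15, both during VR use. Sections 4.0, 5.1 and 5.3 and the Protocol Summary give the device as the source or the session as the time. No section plans a reading at rest.

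**Step 2: what the contrast estimates.** For any measure,

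last − first = (last − rest) − (first − rest).

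Only the left side is observed. One observed quantity cannot identify the two terms on the right.

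**Step 3: example with assumed values.** Suppose the observed last − first is −5 units.

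| Assumed first − rest | Implied last − rest | Reading |
|---|---|---|
| −5 | −5 + (−5) = −10 | Moved further from rest |
| 0 | −5 + 0 = −5 | Moved away from rest |
| +5 | −5 + 5 = 0 | Returned to rest |

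The same result fits all three. If the response is already −5 in minute 1 and stays there, last − first = −5 − (−5) = 0 despite a lasting change.

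**Step 4: two response shapes, for illustration only.** The documents give no response time, so the time constant τ (in minutes) is assumed and varied from 0.1 to 5. Each response has unit size.

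- Sustained response, 1 − exp(−t/τ): first-minute mean = 1 − τ(1 − e^(−1/τ)); last-minute mean = 1 − τ(e^(−14/τ) − e^(−15/τ)). Share captured = (last − first)/last.
- Fading response, exp(−t/τ): the window means are one minus those above.

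| τ (min) | Sustained: first − rest | Sustained: last − rest | Share captured by first-to-last | Fading: first − rest | Fading: last − rest | Fading: last − first |
|---|---|---|---|---|---|---|
| 0.1 | 0.900 | 1.000 | 0.100 | 0.100 | 0.000 | −0.100 |
| 0.5 | 0.568 | 1.000 | 0.432 | 0.432 | 0.000 | −0.432 |
| 1 | 0.368 | 1.000 | 0.632 | 0.632 | 0.000 | −0.632 |
| 2 | 0.213 | 0.999 | 0.787 | 0.787 | 0.001 | −0.786 |
| 5 | 0.094 | 0.945 | 0.901 | 0.906 | 0.055 | −0.851 |

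For a sustained response, the planned contrast captures between 10% and 90% over this range, and 100% if the response begins only after minute 1. For a fading response, the planned contrast does detect change, while last minute versus rest is close to zero. So a baseline compared with the last minute alone would exchange one blind spot for another. Both the first and the last minute need to be set against it.

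**The case against.** The strongest reply is that the plan asks only about change during use. The Aim 2 heading, Section 2.0 and the secondary outcome in Section 4.0 all say so, and the sub-bullet sits under that heading. This largely stands. First versus last minute is a proper measure for those passages and for the planned correlations. A reader might infer that the secondary outcome is invalid or that Aim 2 as a whole cannot be answered; the documents do not support that. What remains is one sub-bullet whose wording reaches further than the only contrast planned for it.

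A second reply is that a reaction to starting VR which then fades is itself an effect with VR use. That is correct. A reader might call such a finding a false positive, but it is not. What is unclear is its direction and meaning.

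A third reply is that a baseline would not establish causation in one arm, where anticipation, settling or the passage of time could also move the readings. This stands too. A baseline supplies the missing reference level and no more.

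Section 5.4 says that only charts will be used for data collection. That conflicts with headset recording elsewhere, but it does not plan a resting reading either.

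**Conclusion.** The point holds as a modest design improvement confined to the first Aim 2 sub-bullet. The identity in step 2 needs no assumption. It shows that the planned contrast can miss an effect already established at the start, and that it cannot say which way a detected change lies relative to rest. That no baseline is planned rests on what the plan states about the source and timing of biodata, as well as on its silence.

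The size of the loss cannot be given. The 10% to 90% range follows from assumed response times, and the conclusion does not depend on it. A reader might go on to infer that the study is underpowered for physiology. The documents do not support that, because they give no physiological effect size, variability or response time, and Section 7.2 ties its sample size to none of the three measures.

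The primary outcomes, the sample size and the planned correlations are untouched. Section 3.3 notes that "patients will be expected to maneuver through questions/steps of the VR system during the session", and the plan does not say whether minute 1 is content or these steps. That is a separate, minor clarification.

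**What to change.** 1. If the headset can record before content starts, add a baseline to Sections 4.0, 5.1 and 7.1: heart rate, heart rate variability and pupil diameter averaged over one minute, headset on, after a brief settling period, with a neutral scene matched in brightness to the content as far as possible.
2. For the sub-bullet, report both first minute versus baseline and last minute versus baseline. Keep first versus last minute as the secondary outcome and for the planned Aim 2 correlations. Label any correlation that uses the baseline as exploratory.
3. State that in a single-arm study these contrasts show change from rest, not that VR caused it, and that pupil results are read with caution where brightness differs.
4. If the device cannot record before content, reword the sub-bullet along these lines: *describe how the three measures change over the course of the session*. Nothing else is then needed for this point.

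The cost is a few bedside minutes and no extra patients. Section 6.1 already places an investigator at the session and has the device record automatically. The downsides are:

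- device capability must be confirmed;
- a brightness difference could itself move pupil diameter (an assumption from general physiology, not from the documents);
- anticipation can affect the baseline;
- a headset-on baseline does not capture any effect of putting the headset on;
- there are more contrasts to report: 3 measures × 2 windows = 6, beside the 3 planned.

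The rewording costs nothing, but it gives up the sub-bullet's broader claim.
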